1.1 Overview

This project will study the efficacy and safety of the pharmacologic blockade of urease in the nitrogen salvage pathway of intestinal microbes in subjects with partial urea cycle disorders. Additional trapping of ammonia as excretable urea may result in improved nitrogen excretion and reduced ammonia levels.

Urea cycle disorders (UCDs) are a group of disorders resulting from a complete or partial deficiency of one of the 6 enzymes or 2 transporters that comprise the urea cycle, the essential biochemical pathway which converts toxic ammonia into urea. These disorders have as a common feature, a reduced or complete inability to convert ammonia into urea, thereby resulting in high ammonia levels, or hyperammonemia. If untreated, hyperammonemia may result acutely in lethargy and coma, and chronically in intellectual disability. Current treatment for hyperammonemia is suboptimal, thus the search for new treatments is critical.

The urease inhibitor, acetohydroxamic acid (AHA, Lithostat®, Mission Pharmacal), is an FDA-approved product for another indication- the treatment of struvite nephrolithiasis in chronic urinary tract infections in both adults and children^{1,2}.

It is known that many urea-splitting bacteria also exist in the gut, and that in healthy individuals, approximately 15-30% of blood urea is degraded via gut bacteria into ammonia³, which returns to the liver via the portal vein, only to be recycled into urea. This percentage of degraded urea may even be greater in patients with urea cycle disorders, who are on a low protein-diet⁴ and whose gastrointestinal contents thus likely have lower nitrogen content, promoting bacterial recycling of nitrogen from available urea. Additionally, urea hydrolysis has been shown to be greatest in infants⁵, precisely the age at which hyperammonemic episodes are the most frequent in UCD patients.

We intend to study if AHA can inhibit gut bacteria degradation of urea, thereby reducing the quantity of ammonia returning to the liver. We intend to investigate this by studying subjects on two occasions at least 3 days apart:

On the first occasion, subjects will receive an intravenous dose of ¹³C-urea. Following the intravenous bolus of ¹³C-urea, over the subsequent 4 hours, we will collect several sequential measurements of blood and urine biomarkers from an IV catheter placed in the other arm. The intent is to obtain baseline ¹³CO₂ kinetics in the subject.

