Enteral AHA has previously been administered to patients with hyperammonemia due to hepatic encephalopathy in two published reports^{6,7}. A single dose of oral 750 mg in adult patients was insufficient to result in any change in ammonia after 90 minutes in cirrhotic subjects free of *H. Pylori*⁷. However, in encephalopathy cirrhotic subjects administered AHA 20-60 mg/kg via naso-gastric tube, a statistically significant decreased in blood ammonia was observed⁶, with the effect most striking in subjects receiving a dose of 40-60 mg/kg/d.

This proposal would introduce a novel therapeutic approach for patients with UCD using a low-toxicity compound that may be particularly effective in patients with partial UCDs. There are two potential ways this approach may lower blood ammonia or excess nitrogen. The first is through blockage of new ammonia formation from urease. The second path may be increased consumption of residual dietary nitrogen by the gut flora in the absence of available nitrogen released through urease. Both effects may decrease the amount of nitrogen entering the portal vein. This new therapy will not interfere with other therapies, but would be complementary to them and may potentiate the nitrogen trapping effects of arginine and citrulline by preventing the degradation of the urea produced by their administration.

4. Study Design and Methods

This pilot crossover study will first evaluate the impact of AHA versus non-AHA primarily on ¹³CO₂ and secondarily on other biomarkers in healthy adults before applying the same crossover design to UCD subjects. A randomization table will determine if AHA or non-AHA will be performed first.

The figure below illustrates our study design:

Subjects will be required to fast for a minimum of 4 hours prior to beginning the study. Food consumption will not be permitted during the study; however subjects will be allowed to drink water or pedialyte throughout the study. Subjects will be observed and

various biomarkers will be collected throughout the 4-6 hours that they are studied. 5 mL of blood will be collected at each of the 7 time points shown above. Administration of [¹³C]-urea will be completed through an intravenous catheter. Blood draws will be done through the placement of a Heplock intravenous catheter on the opposite arm from where [¹³C]-urea was first administered. If there is not adequate vascular access, subjects will have a PICC (peripherally inserted central catheter) line placed instead.

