4.1 Inclusion Criteria

For healthy adults:

- Ages 18-60 years
- Compliant with receiving medications orally and intravenously
- Compliant with providing blood and urine samples

For UCD subjects:

- Ages 18-60 years
- Compliant with receiving medications orally and intravenously
- Compliant with providing blood and urine samples
- Participants should be diagnosed with one of the following 4 urea cycle disorders:
 - o Carbamylphosphate synthetase I deficiency - decreased (less than 20 % of control) CPS I enzyme activity in liver or an identified pathogenic mutation
 - o Ornithine Transcarbamylase deficiency- identification of a pathogenic mutation, linkage analysis in an affected family, less than 20% of control of OTC activity in the liver, or elevated urinary orotate (greater than 20 µM/mM) following allopurinol loading with absence of argininosuccinic acid
 - o Argininosuccinic acid synthetase deficiency (Citrullinemia) - greater than or equal to 10-fold elevation of citrulline in plasma, decreased AS enzyme activity in cultured skin fibroblasts or other appropriate tissue, or identification of a pathogenic mutation in the AS gene
 - o Argininosuccinic acid lyase deficiency - presence of argininosuccinic acid in the blood or urine, decreased AL enzyme activity in cultured skin fibroblasts or other appropriate tissue, or identification of a pathogenic mutation in the AL gene

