4.3 Recruitment of Participants

The institution conducting this study, Children's National Medical Center (CNMC), is a nation-wide referral center for patients with urea cycle disorders and other inborn errors of metabolism. Additionally, CNMC is the lead site of the Urea Cycle Disorders Consortium (UCDC), part of the Rare Diseases Clinical Research Network (RDCRN). UCDC members will refer potential participants to this trial. In addition, the RDCRN-UCDC has established a contact registry that informs registrants of clinical trials. We are in close contact with the National Urea Cycle Disorders Foundation (NUCDF), a lay organization dedicated to the promotion of treatment and research to improve the health of patients with urea cycle disorders. This organization helps with patient recruitment for these studies. Our professional relationship with each of these families is very strong and trusting. We have enrolled some of these patients previously in research studies. We anticipate no problem in accommodating the stipulated patient cohort (maximum of 8 individuals total for the current project). Thus, we hope to be able to recruit a sufficient number of participants (see power calculation and statistical considerations) for this trial both locally and nationally.

The Washington DC area is comprised of a large diverse metropolitan population. We do not anticipate difficulty with recruitment of 8 healthy adult control subjects.

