Urea, and by extension, its stable isotope [¹³C]-urea, is a substance regarded by the FDA to be generally regarded as safe (GRAS). Administration of a small amount of stable isotopic urea should not pose a risk to subjects with urea cycle disorders, as the amount of ammonia generated by its hemolysis would represent only a small fraction of the total body ammonia.

There is a potential risk of contamination of the drug or isotope used in the study. However, a sterile and pyrogen-free preparation of the isotope is used, and the drug is manufactured via Current Good Manufacturing Practices (CGMP).

Study Procedures:

Venipuncture: The placement of the two Heplock intravenous catheters for blood sampling and [¹³C]-urea administration could result in a bruise or infection at the site of insertion. The vein in which the needle has been inserted to draw blood may become sore and red. A temporary “black and blue mark” may develop, and rarely fainting may occur. If a PICC line is inserted in the arm (by an interventional radiologist) intravenous sedation is given and involves risks of apnea or aspiration. There is also risk of vessel perforation and infection of the central line catheter.

There is a risk of loss of confidentiality, which could affect insurability and result in stigmatization.

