10.1 Appendix

Drug Information:

Acetohydroxamic acid (Lithostat)

Pharmacology and Pharmaceutical Information:

Acetohydroxamic acid (AHA) is a stable, synthetic compound derived from hydroxylamine and ethyl acetate. It is a urease inhibitor that reversibly inhibits bacterial enzyme urease, thereby inhibiting the hydrolysis of urea and production of ammonia in urine infected with urea-splitting organisms. AHA is available for oral administration as 250 mg white, round tablets and manufactured by Mission Pharmacal. The intact drug is stored at controlled room temperature (20–25°C)

Treatment Information:

All subjects (healthy adults and UCD patients) will receive a single oral dose of 60 mg/kg acetohydroxamic acid during one of the treatment periods, based on the randomization assignment determining whether treatment occurs in the first or the second treatment cycle; doses will be rounded “up” or “down” to the nearest 250 mg to coincide with the available dosage form since the tablets cannot be scored. Patients will be instructed to fast for 4 hours prior to the study; subsequently, the ¹³C-Urea tracer will be administered 60 minutes after the ingestion of the acetohydroxamic acid dose.

¹³C-Urea

¹³C-Urea is a stable isotope produced by Cambridge Isotope Laboratories, Inc., Tewksbury, MA. The GMP grade pharmaceutical product is provided to Children’s National Medical Center as a sterile bulk powder.

Treatment Information:

All subjects (healthy adults and UCD patients) will receive a single IV infusion of ¹³C-Urea administered over 10-15 minutes, during both treatment cycles. The infusion will be prepared at a dose of 6 mg/kg and infused via a peripheral IV.

Preparation of ¹³C-Urea for Intravenous Use

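### Usable peripheral veins are not an entry criterion and the PICC fallback is open to healthy volunteers, so one of them could have a PICC placed under sedation; the plan also does not say which line the PICC replaces.

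*Combined protocol and SAP*

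**What the plan says.** **Entry criteria.** For intravenous access, the Synopsis and 4.1 ask only that a participant be "Compliant with receiving medications orally and intravenously", with a parallel item on giving blood and urine. These items concern willingness, not veins. The exclusions in the Synopsis and 4.2 do not name venous access. The nearest item is the general one that lets the investigator exclude anyone whom a medical condition or abnormality may put at additional risk.

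**Line set-up.** The Overview (1.1) has samples taken "from an IV catheter placed in the other arm". Section 4 repeats this: "Blood draws will be done through the placement of a Heplock intravenous catheter on the opposite arm from where" the tracer was given. The next sentence is the fallback: "If there is not adequate vascular access, subjects will have a PICC (peripherally inserted central catheter) line placed instead". Section 4 describes a design used first "in healthy adults before applying the same crossover design to UCD subjects", and the fallback has no group limit.

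**Risks.** Section 5.3 plans two Heplock catheters, one for sampling and one for the tracer. It then says that for a PICC, placed by an interventional radiologist, "intravenous sedation is given and involves risks of apnea or aspiration". It adds vessel perforation and infection of the central line.

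**Tracer route.** Appendix 10.1, writing of all subjects in both groups, says: "The infusion will be prepared at a dose of 6 mg/kg and infused via a peripheral IV". It does not mention the PICC case.

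**Recruitment.** Section 4.3 says: "We do not anticipate difficulty with recruitment of 8 healthy adult control subjects".

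**The concern.** The first issue is avoidable risk. Section 8.2.1 sets the study's risks against possible benefit to patients with urea cycle disorders. Healthy volunteers receive payment but have no prospect of treatment benefit. Followed as written, the plan can take such a volunteer from two peripheral catheters to a sedated procedure with a central line, and no entry check is designed to prevent it.

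The second issue is the sampling method. The plan separates infusion and sampling by arm, but its fallback does not say whether that separation survives. Blood 13C-urea is a secondary outcome, and samples drawn through a line that carried the tracer could read too high. Each person is compared across two study days in a group of 8, and under Section 6 the healthy cohort decides whether the study opens in adults with urea cycle disorders. An access problem in one person is therefore not negligible.

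**Working it through.** The plan states no figure on this point, so there is none to reproduce. The check is mainly a comparison of text.

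**Step 1: can a healthy volunteer reach the PICC?**
- Synopsis and 4.1: compliance is required; vein adequacy is not.
- Synopsis and 4.2: no exclusion names venous access; the discretionary exclusion is available but not mandatory.
- Section 4: the fallback applies to *subjects*, in a section covering both groups.
- Section 5.3: the sedation text does not distinguish the groups.

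So yes, unless an investigator chooses to use the discretionary exclusion.

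**Step 2: which line does the PICC replace?** Section 4 says *instead* without saying instead of what.

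| Reading | Peripheral tracer infusion (Appendix 10.1) | Opposite-arm sampling (1.1, Section 4) |
|---|---|---|
| PICC replaces the sampling Heplock only | Stands | Stands |
| PICC replaces the infusion line only | Contradicted | Can stand, if sampling stays in the other arm |
| PICC replaces both, one line for both purposes | Contradicted | Lost; blood 13C-urea could be contaminated |

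The blood-draw Heplock is the subject of the sentence just before the fallback, so the first reading is the most natural. The text does not exclude the others.

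**Step 3: size.**
- Weight of one person: 1/8 = 12.5% of a group (8 per group, Synopsis).
- Days apart: at least 3 (4.6). If a PICC is needed on both days, it either stays in for at least 3 days or is placed twice. The plan does not say which.
- Chance of at least one affected person in 8: 1 - (1 - p)^8, where p is the rate of inadequate access per person. The documents give no p, so the values below are assumptions.
  - p = 0.02: 1 - 0.98^8 = 1 - 0.851 = 0.149
  - p = 0.10: 1 - 0.90^8 = 1 - 0.430 = 0.570

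The assumed range gives about 15-57%. It shows only that the case need not be rare in a group of 8; it does not estimate how often it will arise.

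**The case against.** The strongest reply is that the documents agree on their most natural reading. If the PICC stands in for the blood-draw catheter, the tracer still goes in by peripheral IV in the other arm and nothing in the Appendix is breached. This stands. A reader might infer that the fallback necessarily conflicts with the Appendix and abolishes opposite-arm sampling. The documents do not support that: both consequences depend on a reading that the text permits but does not state.

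A second reply is that the discretionary exclusion already allows such a volunteer to be kept out. This stands in part. Nothing obliges an investigator to use it, and Section 4 provides a different course for exactly this subject.

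A third reply concerns bias. A reader might infer that the primary endpoint is distorted. The primary outcome is blood 13CO2, and nothing in the documents shows that tracer left in a line would raise it. The contamination argument concerns 13C-urea and needs a shared line, which the plan nowhere prescribes. A difference in sedation between the two days is also conjecture, because the plan does not say when a PICC would be placed relative to the study hours. This reply stands.

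Finally, 4.3 speaks of recruiting 8 healthy adults and does not mention replacements, so it gives only indirect support for the view that a screen-out costs little. The consent templates (10.2, 10.3) and the design figure were not available for this check and may say more about PICC use.

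**Conclusion.** Two points hold on the text alone. Venous access is not an entry criterion, and the PICC fallback, with the sedation described in 5.3, is open to healthy volunteers. The only barrier is discretionary. The plan also leaves undefined which line the PICC replaces, so a site cannot tell from it whether the Appendix's infusion route and the separation of arms still apply.

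The consequence is an avoidable procedural risk in Group 1 and an ambiguity in the sampling method. A definite contradiction is not shown, nor is bias in the primary comparison. One affected person would be 12.5% of a group. The 15-57% chance of at least one rests wholly on the assumed 2-10% rate and should not be read as a forecast. The point is worth settling before enrolment; it does not call the primary analysis into question.

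**What to change.** Add adequate peripheral venous access at screening to the Group 1 inclusion criteria, in both the Synopsis and 4.1. It can be confirmed when the site attests to eligibility under 7.1.

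Separately, ask the sponsor to reconcile Section 4, Section 5.3 and Appendix 10.1 on three questions:
- whether the PICC fallback is meant for Group 1;
- which catheter the PICC replaces;
- how infusion and sampling are kept separate on each of the two study days.

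The answers are for the sponsor and investigators, and none is proposed here. They are needed even with the new criterion, because access judged adequate at screening may still fail on the day and because Group 2 remains under the fallback.

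The cost is protocol wording, plus consent wording if the templates describe the fallback. The downside is that an occasional healthy volunteer is screened out. Section 4.3 anticipates no difficulty in finding 8 healthy adults, so the effect on recruitment should be small. The criterion does not change who is eligible for Group 2.

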4.1 Inclusion Criteria

For healthy adults:

- Ages 18-60 years
- Compliant with receiving medications orally and intravenously
- Compliant with providing blood and urine samples

For UCD subjects:

- Ages 18-60 years
- Compliant with receiving medications orally and intravenously
- Compliant with providing blood and urine samples
- Participants should be diagnosed with one of the following 4 urea cycle disorders:
 - o Carbamylphosphate synthetase I deficiency - decreased (less than 20 % of control) CPS I enzyme activity in liver or an identified pathogenic mutation
 - o Ornithine Transcarbamylase deficiency- identification of a pathogenic mutation, linkage analysis in an affected family, less than 20% of control of OTC activity in the liver, or elevated urinary orotate (greater than 20 µM/mM) following allopurinol loading with absence of argininosuccinic acid
 - o Argininosuccinic acid synthetase deficiency (Citrullinemia) - greater than or equal to 10-fold elevation of citrulline in plasma, decreased AS enzyme activity in cultured skin fibroblasts or other appropriate tissue, or identification of a pathogenic mutation in the AS gene
 - o Argininosuccinic acid lyase deficiency - presence of argininosuccinic acid in the blood or urine, decreased AL enzyme activity in cultured skin fibroblasts or other appropriate tissue, or identification of a pathogenic mutation in the AL gene

4.2 Exclusion Criteria

For healthy and UCD Patients:

- Current or prior Helicobacter Pylori infection
- Chronic gastrointestinal illness (e.g., inflammatory bowel disease)
- Chronic renal failure
- Taking probiotic medications within the week prior to the study

- Pregnant or lactating. Documentation of a negative pregnancy test within a week prior to testing is required, unless pre-menarchal or menopausal, experiencing menses that week, or other circumstances which preclude pregnancy (e.g. hysterectomy).
- Presence of acute infection at the time of inclusion
- Participation in any other clinical interventional trial or received experimental medication within the last 30 days
- Any clinical or laboratory abnormality or medical condition that, at the discretion of the investigator, may put the subject at an additional risk by participating in this study

4.3 Recruitment of Participants

The institution conducting this study, Children's National Medical Center (CNMC), is a nation-wide referral center for patients with urea cycle disorders and other inborn errors of metabolism. Additionally, CNMC is the lead site of the Urea Cycle Disorders Consortium (UCDC), part of the Rare Diseases Clinical Research Network (RDCRN). UCDC members will refer potential participants to this trial. In addition, the RDCRN-UCDC has established a contact registry that informs registrants of clinical trials. We are in close contact with the National Urea Cycle Disorders Foundation (NUCDF), a lay organization dedicated to the promotion of treatment and research to improve the health of patients with urea cycle disorders. This organization helps with patient recruitment for these studies. Our professional relationship with each of these families is very strong and trusting. We have enrolled some of these patients previously in research studies. We anticipate no problem in accommodating the stipulated patient cohort (maximum of 8 individuals total for the current project). Thus, we hope to be able to recruit a sufficient number of participants (see power calculation and statistical considerations) for this trial both locally and nationally.

The Washington DC area is comprised of a large diverse metropolitan population. We do not anticipate difficulty with recruitment of 8 healthy adult control subjects.

4.4 Retention strategies

As the study involves only 2 days of participation, we anticipate retention to be near 100%.

4.5 Data Elements

In addition to the elements described in Table 1, the collected data elements will include age, sex, race, and ethnicity, as required by the NIH, as well as UCD diagnosis and method of diagnosis, if relevant.

4.6 Schedule of Events

Subjects will be studied twice: once without and once with a single dose of acetohydroxamic acid, with the two study days at least 3-days apart.

Table 1. Laboratory investigations (each study day)

	Time point (min)							
	Baseline	0	30	60	90	120	180	240
Blood [¹³ C]-urea		X	X	X	X	X	X	X
Blood urea		X	X	X	X	X	X	X
Plasma glutamine		X	X	X	X	X	X	X
Ammonia		X	X	X	X	X	X	X
Blood ¹³ CO ₂		X	X	X	X	X	X	X
Urine [¹³ C]-urea		X						X
Urine urea		X						X
Safety labs:								
Hemoglobin	X							X
White blood count	X							X
Platelets	X							X
AST	X							X
ALT	X							X
Bilirubin	X							X
Creatinine	X							X

'Baseline' indicates at a time 0 on days when AHA is not administered or at a time prior to AHA administration on the days where AHA is administered. In addition, some of the blood and urine samples will be saved at the Clinical and Translational Science Institute at CNMC for up to 3 years after the conclusion of the study to test for the metabolism of AHA, after which the samples will be discarded.

5. Safety Monitoring

